3.3 Number of Subjects

Participants in this clinical investigation shall be referred to as “subjects”. Approximately 1600 subjects will be enrolled in this study.

3.4 Replacement of Subjects

Subjects who are withdrawn or removed from treatment or the study will not be replaced.

3.5 Estimated Study Duration

3.5.1 Study Duration for Subjects

The study will continue for 260 weeks (approximately 5 years).

3.5.2 End of Study

Primary Completion: The primary completion date is defined as the date when the last subject is assessed or receives an intervention for the purposes of final collection of data for the primary endpoint(s), whether the study concluded as planned in the protocol or was terminated early.

The primary completion date is the date when the last subject has completed the assessments for EOS/Safety Follow-up.

If the study concludes prior to the primary completion date originally planned in the protocol (ie, early termination of the study), then the primary completion will be the date when the last subject is assessed or receives an intervention for evaluation in the study (ie, last subject last visit).

End of Study: The end of study date is defined as the date when the last subject is assessed or receives an intervention for evaluation in the study (ie, last subject last visit), following any additional parts in the study (eg, long-term follow-up), as applicable.

4. SUBJECT ELIGIBILITY

Investigators will be expected to maintain a screening log of all potential study candidates that includes limited information about the potential candidate (eg, date of screening). This log may be completed and updated via an Interactive Voice Response (IVR)/Interactive Web Response (IWR) system.

Before any study-specific activities/procedure, the appropriate written informed consent must be obtained (see [Section 11.1](#)).

4.1 Inclusion Criteria

- 101 Subject has provided informed consent prior to initiation of any study-specific activities/procedures.
- 102 Subject had completed FOURIER (Study 20110118) while still receiving assigned Investigational Product.

4.2 Exclusion Criteria

- 201 Permanent discontinuation of Investigational Product during FOURIER for any reason including an adverse event or serious adverse event.
- 202 Currently receiving treatment in another investigational device or drug study, or less than 4 weeks since ending treatment on another investigational device or drug study(ies). Other investigational procedures while participating in this study are excluded.
- 203 Subject likely to not be available to complete all protocol-required study visits or procedures, and/or to comply with all required study procedures to the best of the subject and investigator's knowledge.
- 204 History or evidence of any other clinically significant disorder, condition or disease that, in the opinion of the investigator or Amgen physician, if consulted, would pose a risk to subject safety or interfere with the study evaluation, procedures or completion.
- 205 Subject has known sensitivity to any of the active substances or excipients (eg, sodium acetate) to be administered during dosing.
- 206 Females who are pregnant or breastfeeding or planning to become pregnant or breastfeed during treatment with evolocumab and for an additional 15 weeks after treatment with evolocumab discontinues.
- 207 Female subjects of childbearing potential unwilling to use an acceptable method of effective contraception during treatment and for an additional 15 weeks after the last dose of protocol-required therapies. Refer to [Section 6.8](#) for additional contraceptive information.

5. SUBJECT ENROLLMENT

Before subjects begin participation in any study-specific activities/procedures, Amgen requires a copy of the site's written institutional review board/independent ethics committee (IRB/IEC) approval of the protocol, informed consent form (ICF), and all other subject information and/or recruitment material, if applicable (see [Section 11.2](#)). Subject or the subject's legally acceptable representative must personally sign and date the IRB/IEC and Amgen approved ICF before commencement of study-specific activities/procedures.

A subject is considered enrolled when the investigator decides that the subject has met all eligibility criteria, documents and dates this decision in the subject's medical record, and contacts the IVR/IWR system to enroll the subject.

Each subject who enter into the screening period for the study (after signing the IRB/IEC-approved ICF) are to be assigned the same subject identification number as the parent study (FOURIER Study 20110118) before any study procedures are performed. This number will be used to identify the subject throughout the clinical study and must be used on all study documentation related to that subject.

Approved

The subject identification number must remain constant throughout the entire clinical study; it must not be changed after initial assignment.

5.1 Treatment Assignment

All subjects will receive open-label evolocumab.

The treatment assignment date is to be documented in the subject's medical record and on the enrollment case report form (CRF).

6. TREATMENT PROCEDURES

6.1 Classification of Product(s), Medical Device(s) and/or Combination Product(s)

The Amgen investigational product used in this study includes: evolocumab.

The non-Amgen non-investigational products used in this study includes: background LLTs, including a statin.

The investigational medical devices used in this study includes: prefilled auto-injector/pen (AI/pen) or personal injector (PI).

Note: Non-investigational medical devices (ie, medical device[s] not under study) or medicinal products will be described in [Section 6.5](#).

The Investigational Product Instruction Manual (IPIM), a document external to this protocol, contains detailed information regarding the storage, preparation, destruction, and administration of evolocumab and the investigational medical devices used in this study.

6.2 Investigational Product

6.2.1 Amgen Investigational Product - Evolocumab

Evolocumab will be manufactured and packaged by Amgen Inc., and distributed using Amgen clinical study drug distribution procedures. Evolocumab will be presented as follows:

- an AI/pen, as a single-use, disposable, handheld mechanical (spring-based) device for fixed dose, subcutaneous (SC) injection of a 1.0-mL deliverable volume of 140 mg/mL evolocumab
- a PI, as a single-use, disposable, on-body electromechanical injection device that is copackaged with a prefilled Crystal Zenith cartridge containing a 3.5-mL deliverable volume of 120 mg/mL evolocumab

Evolocumab should be stored refrigerated and protected from light according to the storage and expiration information provided on the label (where required). Evolocumab

should be handled per the instructions provided in the IPIM and the instructions for use (IFU) for the prefilled AI/pen or PI.

The prefilled AI/pen or PI should be inspected for investigational product quality, expiry, and damage before using. Damaged, expired, or degraded product should not be used and any issues with the prefilled AI/pen or PI should be reported to Amgen. Further details are provided in the IPIM and IFU.

Evolocumab will be supplied directly to the site. The method of resupply will be determined based on local regulations as well as available infrastructure. The investigator may be required to record the box number of evolocumab (prefilled AI/pen or PI) on the subject's Drug Administration electronic case report form (eCRF). Subjects should return used evolocumab for reconciliation by the site.

6.2.1.1 Dosage, Administration, and Schedule

Evolocumab will be administered SC Q2W or QM for approximately 260 weeks in accordance with the instructions in the IPIM and IFU. **The last resupply of evolocumab will occur 12 weeks after the week 240 visit.** The subject (or designee, if not a qualified healthcare professional) must have demonstrated competency at administration of SC injections before self-administration is permitted. The first self-administered dose by the subject (or designee, if not a healthcare professional) may be administered at the site under the supervision of a healthcare provider at day 1. In this study, evolocumab will be administered by self-administration by the subject, designee, or a qualified healthcare professional in a non-investigator site setting (eg, at home). In exceptional circumstances, SC administration of evolocumab by a qualified healthcare professional in a clinic setting will also be allowed.

When evolocumab is scheduled to be administered at the study site, the date and completion time of administration, the body location of the injection, whether the injection was fully or partially administered, and box number are to be recorded on each subject's eCRF.

When evolocumab is administered at a non-investigator site location, at a minimum, the dates the devices were dispensed and the used devices returned, the number of devices returned, box numbers, and for each device whether it was returned fully or partially used are to be recorded on each subject's eCRF.

It is suggested that the evolocumab administration is done by the subject under site staff supervision at each of the regular study visits to ensure continued proper use of the

injection device. Evolocumab administration at a scheduled visit, if applicable, is to be performed after completion of the blood draws and vital signs.

Details of preparing evolocumab, the injection procedures, and device disposal are included in the IPIM and IFU provided by Amgen before the start of the study.

Evolocumab will be administered either at 140 mg in 1.0 mL (1 administration by prefilled AI/pen) Q2W or at 420 mg in 3.0 mL or 3.5 mL (3 administrations by prefilled AI/pen or 1 administration by PI, respectively) QM. The 3 injections for the QM administration, if applicable, can be administered into different injection sites. The SC injections should be administered in a consecutive fashion with all injections completed within 30 minutes.

The effects of overdose of this product are not known.

6.2.1.2 Dosage Adjustments, Delays, Rules for Withholding or Restarting, Permanent Discontinuation

No dose adjustments of evolocumab will be allowed in this study.

Evolocumab is administered on a Q2W or QM schedule. Subjects will have the opportunity to switch between the AI/pen and PI, at any scheduled time point where evolocumab is supplied to the subject, provided the appropriate supply is available. **The first self-administration after switching the device should be done at a regularly scheduled visit under the supervision of the investigator or qualified study center staff.** Subjects who choose QM treatment will initiate treatment using the PI, provided the appropriate supply is available. If the PI is not available, then the AI/pen may be used. Additionally, subjects taking 420 mg evolocumab QM will have the opportunity to switch drug administration (3 administrations by prefilled AI/pen or 1 administration by PI) at any scheduled time point. The reason for dose change of evolocumab is to be recorded on each subject's eCRF(s).

If, in the opinion of the investigator, a subject is unable to tolerate evolocumab, that subject will discontinue evolocumab but should continue to return for all other study procedures and measurements until the EOS.

If a subject dose of evolocumab is missed or late, administration should occur as soon as possible if there are 7 days or more until the next scheduled dose. If there are less than 7 days before the next scheduled dose, the missed dose should be omitted and the next dose should be administered according to the original schedule.

The decision to rechallenge the subject after therapy changes should be discussed and agreed unanimously by the subject, investigator, and Amgen. If signs or symptoms

recur with rechallenge of evolocumab, then evolocumab should be permanently discontinued.

Information on when to stop Amgen investigational product due to hepatotoxicity is provided in [Section 6.3](#).

6.2.2 Non-Amgen Non-investigational Product

Non-Amgen non-investigational products including background LLT (including statin), will also be used in this study. These therapies will not be provided or reimbursed by Amgen.

6.2.2.1 Non-Amgen Non-investigational Product – Background Lipid-lowering Therapy

6.2.2.1.1 Dosage, Administration, and Schedule

It is recommended that subjects continue the same background LLT, including statin, as taken while in FOURIER (Study 20110118). All background LLT adjustments must be clearly documented and recorded on the appropriate eCRF page and in the source documents. The dose, start date/time, stop date/time, frequency, and non-Amgen non-investigational product are to be recorded on each subject's eCRF. Background LLT will not be provided by Amgen unless required by local regulations.

Recommendations for background LLT are provided in [Appendix D](#).

All other drugs that are allowed per protocol and that are prescribed for the subject must be commercially available and used at dosages approved by local regulatory authorities.

Subjects should consult the investigator if they miss a dose of background statin.

6.2.2.2 Dosage Adjustments, Delays, Rules for Withholding or Restarting, Permanent Discontinuation

The investigator should consult the local product label for information on dose adjustments, delays, withholding, restarting, or permanent discontinuation of background LLT, including statins. The reason for dose change of non-Amgen non-investigational product is to be recorded on each subject's eCRF(s).

If a subject has elevated ad hoc laboratory values ([Section 6.3](#)) and is receiving background LLT, including statins, that may result in such elevations (eg, ezetimibe, fenofibrate, or niacin), the additional therapies should be evaluated for a potential role in the elevated laboratory values and considered for discontinuation. If a subject has elevations in triglycerides > 500 mg/dL (5.65 mmol/L) and is concomitantly receiving a

bile acid binding resin, the bile acid binding resin should be evaluated for discontinuation.

The decision to rechallenge the subject after therapy changes should be discussed and agreed unanimously by the subject, investigator, and Amgen. If signs or symptoms recur with rechallenge of statin background therapy, the statin may be substituted by another statin in consultation with the Amgen medical monitor, if possible, or the statin therapy may be discontinued. If signs or symptoms recur with rechallenge of other applicable lipid background therapy, this therapy may be discontinued.

6.3 Hepatotoxicity Stopping and Rechallenge Rules

Routine hepatic laboratory assessments are not required for this study. However, the guidelines ([Section 6.3.1](#)) apply for elevated liver enzymes noted during ad hoc tests.

Subjects with abnormal hepatic laboratory values (ie, alkaline phosphatase [ALP], aspartate aminotransferase [AST], alanine aminotransferase [ALT], total bilirubin [TBL]) and/or international normalized ratio [INR] and/or signs/symptoms of hepatitis [as described below]) may meet the criteria for withholding or permanent discontinuation of Amgen investigational product or other protocol-required therapies as specified in the Guidance for Industry Drug-Induced Liver Injury: Premarketing Clinical Evaluation (July 2009).

6.3.1 Criteria for Withholding and/or Permanent Discontinuation of Amgen Investigational Product and Other Protocol-required Therapies Due to Potential Hepatotoxicity

The following stopping and/or withholding rules apply to subjects for whom another cause of their changes in liver biomarkers (TBL, INR and transaminases) has not been identified.

Important alternative causes for elevated AST/ ALT and/or TBL values include, but are not limited to:

- Hepatobiliary tract disease
- Viral hepatitis (eg, Hepatitis A/B/C/D/E, Epstein-Barr Virus, cytomegalovirus, Herpes Simplex Virus, Varicella, toxoplasmosis, and Parvovirus)
- Right sided heart failure, hypotension or any cause of hypoxia to the liver causing ischemia.
- Exposure to hepatotoxic agents/drugs or hepatotoxins, including herbal and dietary supplements, plants and mushrooms

Approved

- Heritable disorders causing impaired glucuronidation (eg, Gilbert's Syndrome, Crigler Najjar syndrome) and drugs that inhibit bilirubin glucuronidation (eg, indinavir, atazanavir)
- Alpha-one antitrypsin deficiency
- Alcoholic hepatitis
- Autoimmune hepatitis
- Wilson's disease and hemochromatosis
- Nonalcoholic Fatty Liver Disease including Steatohepatitis (NASH)
- Non-hepatic causes (eg, rhabdomyolysis, hemolysis)

If investigational product(s) is/are withheld, the subject is to be followed according to recommendations in [Appendix A](#) for possible drug-induced liver injury (DILI).

Rechallenge may be considered if an alternative cause for impaired liver tests (ALT, AST, ALP) and/or elevated TBL, is discovered and the laboratory abnormalities resolve to normal or baseline ([Section 6.3.2](#)).

Table 1. Conditions for Withholding and/or Permanent Discontinuation of Amgen Investigational Product and Other Protocol-required Therapies Due to Potential Hepatotoxicity

Analyte	Temporary Withholding	Permanent Discontinuation
TBL	> 3x upper limit of normal (ULN) at any time	> 2x ULN
		OR
INR	--	> 1.5 (for subjects not on anticoagulation therapy)
	OR	AND
AST/ALT	> 8x ULN at any time > 5x ULN but < 8x ULN for ≥ 2 weeks > 5x ULN but < 8x ULN and unable to adhere to enhanced monitoring schedule > 3x ULN with clinical signs or symptoms that are consistent with hepatitis (such as right upper quadrant pain/tenderness, fever, nausea, vomiting, jaundice).	In the presence of no important alternative causes for elevated AST/ALT and/or TBL values > 3x ULN (when baseline was < ULN)
	OR	
ALP	> 8x ULN at any time	--

ALP = alkaline phosphatase; ALT = alanine aminotransferase; AST = aspartate aminotransferase; INR = international normalized ratio; TBL = total bilirubin; ULN = upper limit of normal

Approved

6.3.2 Criteria for Rechallenge of Amgen Investigational Product and Other Protocol-required Therapies After Potential Hepatotoxicity

The decision to rechallenge the subject should be discussed and agreed upon unanimously by the subject, investigator, and Amgen.

If signs or symptoms recur with rechallenge, then evolocumab, statins, and other applicable lipid background therapies should be permanently discontinued. Subjects who clearly meet the criteria for permanent discontinuation (as described in [Table 1](#)) should never be rechallenged.

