Appendix D. Recommended Lipid-lowering Background Therapy

It is recommended that subjects continue the same background lipid-lowering therapy (LLT), including statin, as taken during FOURIER. Background LLT should be optimized for the individual subject consistent with local professional society guidelines. All subjects should receive at least an effective statin dose, ie, at least atorvastatin 20 mg daily or equivalent. Where locally approved, highly effective statin therapy, defined as at least atorvastatin 40 mg daily or equivalent, is recommended.

No other lipid therapy is required for the FOURIER OLE study. Ezetimibe and other commercially available lipid therapy at dosages approved by local regulatory authorities may be added to any of these regimens except excluded medication as per [Section 6.7](#). These therapies, including statins, are not provided or reimbursed by Amgen (except if required by local regulation). Background LLT received at enrollment should remain unchanged throughout the entire duration of the study.

Approved

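### Protocol 6.2.2.2 permits switching statins when signs or symptoms recur on rechallenge, with no hepatic exception, while 6.3.2 says statins should then be permanently discontinued

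*Protocol*

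**What the plan says.** Two parts of the protocol deal with a recurrence on rechallenge that involves the background statin.

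**Section 6.3.2**, whose heading limits it to rechallenge after potential hepatotoxicity: "If signs or symptoms recur with rechallenge, then evolocumab, statins, and other applicable lipid background therapies should be permanently discontinued". It also bars rechallenge altogether for some subjects ("Subjects who clearly meet the criteria for permanent discontinuation", as set out in Table 1).

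**Section 6.2.2.2**, on dose changes, withholding and restarting of background lipid-lowering therapy. Its second paragraph opens with "If a subject has elevated ad hoc laboratory values ([Section 6.3](#)) and is receiving background LLT, including statins" and asks that therapies which may have caused the elevation be considered for discontinuation. Its third paragraph covers rechallenge after therapy changes. If signs or symptoms recur on the statin, "the statin may be substituted by another statin in consultation with the Amgen medical monitor, if possible, or the statin therapy may be discontinued". For the rest: "If signs or symptoms recur with rechallenge of other applicable lipid background therapy, this therapy may be discontinued".

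The matching section for evolocumab, 6.2.1.2, has its own recurrence rule, which is permanent discontinuation, and a closing pointer: "Information on when to stop Amgen investigational product due to hepatotoxicity is provided in" Section 6.3.

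**The concern.** The same trigger, recurrence of signs or symptoms on rechallenge, leads to two different instructions. One directs that statins be stopped for good. The other allows a different statin to be started. An investigator managing the statin would naturally open 6.2.2.2. The paragraph that sends the reader to Section 6.3 for the laboratory values is followed at once by the permission to switch, and nothing there says that a hepatic recurrence is handled elsewhere.

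What is at stake is a subject-level safety instruction. A subject whose liver signs return on rechallenge could be given another statin by a site relying on an express permission in the protocol, against the hepatic-specific rule.

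**Working it through.** No arithmetic applies. The check is whether the two texts cover the same event, whether they differ, and whether anything ranks them.

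| | 6.2.2.2, third paragraph | 6.3.2 |
|---|---|---|
| Scope | Rechallenge after therapy changes; any signs or symptoms | Rechallenge after potential hepatotoxicity (heading) |
| Statin on recurrence | May be replaced by another statin, or may be stopped | Should be permanently stopped; no substitution offered |
| Other lipid therapy on recurrence | May be stopped | Should be permanently stopped |
| Evolocumab on recurrence | Not addressed | Should be permanently stopped |
| Exception or precedence | None | None over 6.2.2.2 |

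1. **Overlap.** The 6.2.2.2 paragraph is general and also serves non-hepatic complaints. It does not exclude hepatic ones. The therapy changes it refers back to include those made when "If a subject has elevated ad hoc laboratory values" under Section 6.3, and that section is about liver tests. A hepatic recurrence on a restarted statin therefore falls within both texts.

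2. **Difference.** The conflict runs one way. Stopping the statin satisfies both sections, because 6.2.2.2 only says what may be done. Switching is allowed by 6.2.2.2 and departs from 6.3.2. Other lipid therapy follows the same pattern: continuing it fits the permissive wording and departs from 6.3.2.

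3. **Ranking.** The reference to Section 6.3 in the second paragraph of 6.2.2.2 identifies the laboratory values. It does not hand recurrence over to 6.3.2. No other sentence in the protocol does so.

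4. **Evolocumab.** There is no conflict. Sections 6.2.1.2 and 6.3.2 both call for permanent discontinuation on recurrence, and 6.2.1.2 refers hepatotoxicity stopping to Section 6.3.

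5. **How a subject reaches this point.** Liver tests are done only ad hoc (6.3). Section 6.3.1 says rechallenge may be considered if an alternative cause is discovered and the abnormalities return to normal or baseline. Those who clearly meet the permanent-discontinuation criteria are never rechallenged. The subject, the investigator and the sponsor must all agree to the rechallenge. Signs or symptoms must then recur. Each step narrows the group, and the documents give no rate for any of them.

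6. **Analyses.** The planned analyses are descriptive and no estimate depends on which rule is followed. SAP 9.6.4 reports the incidence of changes in background lipid-regulating medication, without a rule that turns on 6.2.2.2 or 6.3.2.

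**The case against.** The best reply is that the specific rule governs the general one. The heading of 6.3.2 confines it to potential hepatotoxicity, 6.2.2.2 is only permissive, and a site can comply with both by stopping the statin. On that view the protocol merely lacks a cross-reference. Much of this stands: a careful reader would probably let 6.3.2 govern. But that is an inference, and a liver-safety instruction should not depend on it when the other section grants an express permission.

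The safeguards also count. Besides the conditions on rechallenge, 6.2.2.2 sends investigators to the local product label for restarting or discontinuing a statin, and it asks for consultation with the medical monitor, if possible, before a substitution. These make an unnoticed switch unlikely. They do not settle the wording: the unanimous agreement is about whether to rechallenge, not what to do after recurrence, and the consultation step does not mention 6.3.2.

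A reader might go further and infer that Appendix D pushes sites towards switching, because it says "All subjects should receive at least an effective statin dose, ie, at least atorvastatin 20 mg daily or equivalent". The documents do not support that. The same appendix says that background therapy received at enrollment should stay unchanged, which weighs against a switch just as much. It is also a general recommendation that does not address hepatic events.

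**Conclusion.** Wrong as written, as a conflicting safety instruction, and of low severity. For recurrence after potential hepatotoxicity, 6.2.2.2 allows a step that 6.3.2 rules out, and the text does not say which section prevails. The conclusion rests on the wording alone: that the general paragraph of 6.2.2.2 reaches hepatic cases because it does not exclude them, and that 6.3.2 offers no substitution.

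Very few subjects, possibly none, would be affected. A reader might want a number or infer a material risk across the planned 1600 subjects. The documents give no incidence of liver events, rechallenge or recurrence, so any count would be built wholly from assumptions. Nor do they support reading the conflict as touching the evolocumab instructions, an endpoint or a planned analysis.

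**What to change.** In the third paragraph of Protocol 6.2.2.2, add to the recurrence rule: *except after potential hepatotoxicity, where Section 6.3.2 applies*. Place it so that it covers both the statin sentence and the sentence on other lipid therapy.

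The exception should use the term in the heading of 6.3.2 and not be tied to a Table 1 threshold. Section 6.3.2 states no such limit on its recurrence rule. Adding one would expressly leave lesser liver elevations under the permissive rule, although Appendix A already asks for close observation once AST or ALT exceeds 3 times the upper limit of normal, below the Table 1 withholding levels for subjects without symptoms. That would be a new clinical choice, not a clarification.

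The cost is one clause in the next amendment or a site clarification letter. It adds no tests, visits or subjects and no new restriction, since 6.3.2 already directs that statins be stopped. Switching statins for non-hepatic complaints remains available.
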